5.2.2 Protocol pharmacology sampling visit schedule

On protocol-specified clinic visits (described below and Table 5), a blood sample will be collected from an arm vein for plasma/WB/RBC/DBS/PBMC isolation and safety laboratories. Hair will be cut from the scalp for comparison with other drug measures. Adverse events will be assessed. All protocol-specified clinic visits are detailed below. Each protocol-specified clinic visit will have a window of up to three days for sample collection (up to a week for hair).

Clinic visit 1: Study entry visit (must be within 30 days after screening visit)

- Medical, sexual, contraception, antenatal and vaccine history review
- Obtain study blood work: WB, DBS, PBMC, plasma, (pre-drug for endogenous molecules such as nucleosides)
- Urine β HCG
- Study urine: (baseline endogenous molecules such as nucleosides)
- STI tests (CT, GT, syphilis)
- hDNA
- Vaginal swab
- Dispense back up PrEP medication: subject home supply
- Dispense study dosing calendar
- DOT: Witness first PrEP dose

Clinic visit 2: Week 1 Dose 4 visit (for 2 doses per week group this will be 4 days since first dose:

- Study Bloodwork: WB, DBS, PBMC, plasma
- Study urine
- Finger stick for DBS
- Cervicovaginal biopsy: Random **subset (50%) of non-pregnant cohort only**
- Vaginal swab
- Medical, sexual, contraception, antenatal and vaccine history review
- AE assessment
- Concomitant Medication Review
- DOT

Clinic visit 3: Week 1 (Dose 7) visit:

- Study bloodwork: WB, DBS, PBMC, plasma
- Study urine
- Finger stick for DBS
- Vaginal biopsy: **Random subject (50%) of non-pregnant cohort only**
- Vaginal swab
- Blood work: hDNA for those who consent to drug transport gene testing.
- Medical, sexual, contraception, antenatal and vaccine history review
- AE assessment
- Concomitant Medication Review
- DOT

Clinic visit 4: Week 2 (Dose 14) visit:

- Study bloodwork: WB, DBS, PBMC, plasma
- Study urine
- Medical, sexual, contraception, antenatal and vaccine history review
- AE assessment
- Concomitant Medication Review
- DOT

Clinic visit 5: Week 3 (Dose 21) visit:

- Study bloodwork: WB, DBS, PBMC, plasma
- Study urine
- Medical, sexual, contraception, antenatal and vaccine history review
- AE assessment
- Concomitant Medication Review
- DOT

Clinic visit 6: Week 4 (Dose 28) visit:

- HIV rapid test
- Urine β HCG
- Study bloodwork: WB, DBS, PBMC, plasma
- Study urine
- Vaginal biopsy: **Non-pregnant cohort only**
- Vaginal swab
- Hair collection
- Urine pregnancy test
- Medical, sexual, contraception, antenatal and vaccine history review
- AE assessment
- Concomitant Medication Review
- DOT
- Finger stick for DBS

Clinic visit 7: Week 5 (Dose 35) visit:

- Study bloodwork: WB, DBS, PBMC, plasma
- Study urine
- Medical, sexual, contraception, antenatal and vaccine history review

- AE assessment
- Concomitant Medication Review
- DOT

Clinic visit 8: Week 6 (Dose 42) visit:

- Study bloodwork: WB, DBS, PBMC, plasma
- Medical, sexual, contraception, antenatal and vaccine history review
- AE assessment
- Concomitant Medication Review
- DOT
- Study urine

Clinic visit 9: Week 7 (Dose 49) visit:

- Study bloodwork: WB, DBS, PBMC, plasma
- Study urine
- Medical, sexual, contraception, antenatal and vaccine history review
- AE assessment
- Concomitant Medication Review
- DOT

Clinic visit 10: Week 8 (Dose 56) visit:

- HIV rapid test
- Urine β HCG
- Study bloodwork: WB, DBS, PBMC, plasma
- Finger stick for DBS
- Study urine
- Vaginal biopsy: **Non-pregnant cohort only**
- Vaginal swab
- Hair collection
- Safety Labs: Creatinine
- Medical, sexual, contraception, antenatal and vaccine history review
- AE assessment
- Concomitant Medication Review
- DOT

Post DOT PrEP visits (Week 9): One visit (Clinic visit #11) within week 9, at least 48 hours after the last DOT PrEP dose.

- Study bloodwork: plasma, WB, DBS, PBMC
- Study urine

Post DOT PrEP visits (Week 10-16): One visit (Clinic visit #12) at least 7 days after week 9 visit (i.e., the visit can occur any time between 2-8 weeks after the last DOT F/TAF PrEP which is about week 10 and week 16 since enrollment)

- Study bloodwork: plasma, WB, DBS, PBMC
- Study urine
- Hair collection

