3.1 Inclusion Criteria

This study will enroll young Kenyan cisgender women (aged 18-30 years old). Cisgender women bear the greatest burden for HIV infection; thus, the study will focus solely on cisgender women. HIV incidence is greatest in younger cisgender women, as is PrEP interest in accumulating data from Kenya, and the age limitation reflects that clinical and epidemiologic need. Enrollment criteria will be finalized at the time of protocol development to account for any updates to Kenyan national guidelines, but the central clinical criteria are as follows:

For all cisgender women

- Age ≥ 18 and ≤ 30 years old
- Willing to undergo urine pregnancy tests
- Has understood the information provided and has provided written informed consent before any study-related procedures are performed.
- HIV uninfected based on negative HIV rapid tests, according to Kenyan national algorithm
- Normal renal function (estimated glomerular filtration rate >60 mL/min)
- Hepatitis B surface Ag negative
- No active clinically significant medical or psychiatric conditions that would interfere with study participation
- Lack of severe anemia
- Willing to use DOT and come to clinic frequently for DOT PrEP for at least 8 weeks
- Willing to have home visits for follow up
- Has an active smartphone to allow off-site observation of dosing
- Intention to stay within the study site's catchment area for at least 8 weeks.
- Resides or works in catchment area with high speed internet coverage to permit video streaming

Specific for non-pregnant cisgender women cohort

- Not pregnant or breast feeding
- At low risk for HIV. *In Kenya, national guidelines define substantial risk for HIV and recommend PrEP be an option for individuals reporting: partner of HIV-infected person not on ART or on ART for <6 months, >1 partner of unknown status, transactional sex, recent STI, recurrent PEP use, inconsistent condom use, or injection drug use. So, non-pregnant cisgender women reporting any of these factors will not be eligible for the study but will be linked for PrEP at clinic of choice including at Thika Site itself.*
- Willing to be randomized to non-daily PrEP and come to clinic frequently for DOT PrEP
- Willingness and ability to be abstinent for at least 7 days after each vaginal biopsy visit.

Specific for pregnant cisgender women only

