3.2 Exclusion Criteria

For all cisgender women

- Inability to give informed consent
- Positive screening HIV+ as determined by standard rapid serologic assays or suspected acute HIV infection in the opinion of the clinician. (example signs and symptoms of acute HIV infection include combinations of fever, headache, fatigue, arthralgia, vomiting, myalgia, diarrhea, pharyngitis, rash, night sweats, and adenopathy cervical or inguinal)
- Positive HBV surface antigen test at screening
- Calculated creatinine clearance < 60 ml/min.
- Any laboratory value or uncontrolled medical conditions that, in the opinion of the investigators, would interfere with the study conditions such as, heart disease and/or cancer.
- Prohibited concomitant medications are: investigational agents (within 30 days of enrollment), aminoglycosides, ganciclovir/valganciclovir, chronic high-dose acyclovir/valacyclovir (>800mg acyclovir or > 500mg valacyclovir for >7 days), cyclosporine, amphotericin B, foscarnet, and cidofovir, and products with same or similar active ingredients as the study medications including TAF®, ATRIPLA®, COMPLERA®, EMTRIVA®, VIREAD®; or drugs containing lamivudine or adefovir, which are close analogs of FTC and tenofovir, respectively.
- Current or past use of PrEP (pre-exposure prophylaxis)
- Not willing to have home visits

Specific for non-pregnant cisgender women cohort

- Pregnancy or plan to become pregnant in the next 6 months or unwillingness to use birth control
- Current breastfeeding
- High risk of HIV infection (for example: sexually active with an HIV infected partner; engages in condomless intercourse with HIV-infected partners or partner of unknown status during the study; females who exchange sex for money, shelter, or gifts; active injection drug use or during the last 12 months; newly diagnosed sexually transmitted infections in last 6 months.

Specific for pregnant cisgender women cohort

- Mother has a known history of any of the following, as determined by the site investigator or designee based on maternal report and available medical records:
- Sick cell anemia (excluding sick cell trait), chronic bleeding, blood transfusion within the past 120 days (excluding for chronic illness) or other blood dyscrasias
- Fetus has a known or suspected major congenital anomaly, from chart review of prior data, defined ultrasound.
- Complications in prior pregnancies that would be considered exclusionary

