5.2 Enrollment and Follow up Procedures

Up to 72 evaluable HIV uninfected participants (54 non pregnant and 18 pregnant cisgender women) will be enrolled and followed up for 16 weeks: 8 weeks with DOT PrEP, and up to 8 weeks for post drug kinetics sampling – one visit in week 9 and an additional visit within weeks 10 to 16 (i.e. 2 visits in total). Enrollment must occur within 30-day screening window. An eligible participant who is unable to schedule a study entry visit within the 30-day screening window must be re-screened prior to entry into the study. All enrolments will be scheduled on specific days to avoid confusion in implementing the proposed dosing and sampling scheme. Study entry visit (enrollment) through week 8 visit will include an adverse effect questionnaire along with medical and medication review. Safety labs and vitals can be ordered as needed at any visit.

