7.5 Randomization and Blinding Procedures

The study design for non-pregnant cohort will be an open-label, randomized study with three arms. The randomization assignments cohort will be made at enrollment if the participant is eligible and agrees to enroll. Randomization will be according to the PrEP dosing frequency and vaginal tissue collection plan (either sampling day 4 or day 7) 1:1:1 fashion programmed by the study statistician and generated from REDcap. Randomization will be done at enrollment.

The allocation of participants for the 3 study arms will be the following:

	2 doses per week	4 doses per week	7 doses per week	Total
Total	18	18	18	54

The study design for the pregnant cohort will be an open-label, non-randomized study with only DOT PrEP daily dosing regimen (7 doses per week).

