want and might benefit from it), all pregnant cisgender women will be at high risk for HIV and will receive only daily PrEP dosing (7 doses per week). HIV risk and eligibility will be determined according to the Kenya guidelines for PrEP. Pregnant cisgender women will receive only daily PrEP dosing (7 doses per week). After 8 weeks of DOT PrEP, pregnant cisgender women will be linked to continue PrEP at the clinic of their choice, including at the Thika site clinic itself, permitting seamless access to PrEP and continuation after the study. For the initially non-pregnant cisgender women, if they become pregnant, study drug will be discontinued unless they have an indication for PrEP for which daily dosing will be provided. Cisgender women will be followed to obtain pregnancy outcomes until end of study.

Reducing social harm risks

In addition to protecting the privacy of participants, as described above, we will monitor for social harms. Social harms will be recorded on separate case report forms. Severe unexpected social harms will be considered unexpected problems and reported to the IRB according to local regulations. Social harms will be included on summary reports for the PSRT, as described in this protocol.

Reducing risks behavior disinhibition

We will use brief standardized questionnaires, which we have used for prior studies in cisgender women to explore partner number, sexual frequency, and condom use over time. Each visit will include risk-reduction counseling for all cisgender women and cisgender women will be provided with condoms. Importantly, only cisgender women at low risk of HIV will be enrolled in the non-pregnant cohort which has potential for assignment for non-daily dosing.

Reducing risks from other study procedures

The blood will be collected from an arm vein, and/or by finger stick, by trained staff at the study site according to standard medical procedures. Hematology will be monitored. The hair that is cut will be taken from underneath the top layer of hair to minimize the ability to see where the hair was cut from and to avoid sun-bleached hair.

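### In the non-pregnant cohort the only STI tests are taken at the entry visit, with no rule that results be known before randomisation and the first dose, although a newly diagnosed STI is a listed marker of excluded HIV risk

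*Combined protocol and SAP*

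**What the plan says.** Eligibility, non-pregnant cohort. Section 3.1 requires low HIV risk, names a recent STI among the national risk indicators, and says that "non-pregnant cisgender women reporting any of these factors will not be eligible for the study". Section 3.2 excludes high HIV risk and gives as one example "newly diagnosed sexually transmitted infections in last 6 months".

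Testing. The screening list in section 5.1 has a blood count, hepatitis B surface antigen, creatinine, HIV and a urine pregnancy test, but no STI test. Section 5.2.2 puts "STI tests (CT, GT, syphilis") at clinic visit 1. The STI row of Table 5 has one mark, under Entry.

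Assignment and dosing. Section 5.2 treats entry and enrolment as the same visit: "Study entry visit (enrollment) through week 8 visit will include an adverse effect questionnaire". Section 7.5 says "Randomization will be done at enrollment", and sets the condition: "The randomization assignments cohort will be made at enrollment if the participant is eligible and agrees to enroll". Clinic visit 1 ends with "DOT: Witness first PrEP dose".

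Safeguard. Section 8.5 states that "only cisgender women at low risk of HIV will be enrolled in the non-pregnant cohort which has potential for assignment for non-daily dosing". Sections 2.5.1 and 8.4 make the same argument after noting that national and WHO guidance recommends only daily PrEP for vaginal exposure.

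**The concern.** A test that bears on an exclusion normally has to be read before the woman is assigned. Here the sample is scheduled for the visit at which she is assigned and dosed, and the protocol does not say that the result must be in hand. An infection that has never been diagnosed cannot be reported at screening, so the study's own test is the only step that would find it.

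What is at stake is participant protection and clean eligibility. The protocol defends the 2- and 4-dose arms by enrolling only low-risk women. On the schedule as written, a woman can hold one of those assignments when her entry sample shows a marker that the protocol itself lists as high risk. The site would then have no written rule on whether she met the criteria, whether she counts as evaluable, or whether she is replaced.

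**Working it through.** The plan states no figure on this point, so there is nothing to reproduce. The check is of the order of procedures, followed by an illustration of scale.

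**Order of procedures**

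1. Screening (5.1, Table 5): no STI test. The STI criterion can be applied only to history.
2. Entry (5.2, 5.2.2, 7.5): STI samples, randomisation, dispensing of the home supply and the first observed dose all fall at one visit.
3. Result before assignment: no section requires it, specifies a same-day test, or gives a turnaround time.
4. Comparison with other test-based criteria: HIV, hepatitis B, creatinine and pregnancy are all tested at screening. For the fetal ultrasound, section 5.1 does require the result by enrolment. STI results have no matching sentence.
5. After assignment: section 8.13 provides for review of infections acquired during the study, and its list of reasons for discontinuation is open-ended. Section 6.1 gives the safety review team questions of eligibility. Neither section states what follows when the entry sample itself is positive.
6. Replacement (3.8): the triggers are missed doses or samples, permanent discontinuation of observed dosing, and pregnancy. A positive STI test is not among them.

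The pregnant cohort is not affected. There a recent STI is a qualifying risk indicator (2.5.2, 3.1), and dosing is daily only.

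**Scale**

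Section 7.5 allocates 18 women to each arm, so 2 × 18 = 36 women are on 2 or 4 doses per week. Let p be the prevalence of undiagnosed STI at entry among women who pass screening. The documents do not give p; the values below are assumptions. The calculation takes women as independent, the test as accurate, and results as arriving after assignment.

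Expected cases = 36 × p. Chance of at least one = 1 − (1 − p)^36.

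| Assumed p | Expected cases among 36 | Chance of at least one |
|---|---|---|
| 1% | 0.36 | 30% |
| 2% | 0.72 | 52% |
| 5% | 1.8 | 84% |
| 10% | 3.6 | 98% |
| 20% | 7.2 | above 99.9% |

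The gap in the sequence does not depend on p. Only the number of women affected does.

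**The case against.** The strongest reply is that the inclusion criterion works on what a woman reports, and that the STI item in 3.2 is only an example of high risk. A woman with an undiagnosed infection satisfies 3.1 as written on the day she is assessed. The entry test may be meant for baseline description and treatment, since STI treatment is part of the prevention package in 2.5.1 and 8.4. This stands in part. A reader might infer that such a woman never qualified, but the documents do not support that, because they never say whether the study's own result counts. The wording in 3.2 is not limited to self-report either, so the question is open.

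Second, the order of steps within the visit is not given. Section 5.2.2 lists the STI tests above dispensing and dosing, and 7.5 randomises only eligible women, so a site could wait for rapid results. That is possible, but not required.

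Third, other protections exist: the risk score used in recruitment (8.5), monthly HIV testing, counselling, condoms and STI treatment, together with investigator withdrawal (3.7) and the review routes in 6.1 and 8.13. It would be wrong to say that the protocol leaves no route for a positive entry result. These measures limit the consequence, but the route is discretionary and comes after assignment.

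Fourth, prevalence may be low, because women reporting inconsistent condom use, transactional sex or a recent STI are already screened out. That is fair, and it is why the range starts at 1%. A reader might also infer that positive tests would use up the replacement margin of 72 − 60 = 12 women. The documents do not establish this, since 3.8 does not make a positive test a trigger; replacement would follow only if the woman then stopped observed dosing for good. Nor does any section tie STI status to biopsy eligibility.

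**Conclusion.** The point holds as a gap in sequence and definition. The only STI tests are scheduled at the visit at which non-pregnant women are randomised and first dosed, with no requirement that results come first. A woman with an undiagnosed STI can therefore be assigned 2 or 4 doses per week before the study's own result is known, which undercuts the stated low-risk safeguard.

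The number affected rests on an assumed prevalence: about 0.4 to 7 of 36 women at 1% to 20%, and none at a site that reads results before assigning. A reader might infer damage to the primary analyses. No bias to the concentration endpoints is shown, and the case for change rests on participant protection and on clear eligibility and evaluability rules.

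**What to change.** Reconcile sections 3.1, 3.2, 5.1, 5.2.2, Table 5 and 7.5 as follows:

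- For the non-pregnant cohort, move the STI tests, exactly as the protocol lists them, from clinic visit 1 to the screening visit.
- State in 7.5 that results must be available before randomisation in that cohort.
- State in 3.2 whether a positive study result counts as a newly diagnosed STI for the exclusion.
- State in 3.8 how a positive result that becomes known only after randomisation affects evaluability and replacement.

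The cost is modest: the tests are already planned, so the additions are tests for women who then fail screening, and some extra screen failures. There is one real downside. With a 30-day screening window, up to 30 days can pass between test and entry, so an infection acquired in that interval would be missed and the entry-day baseline would be lost. Clinical management of a woman who tests positive is for the sponsor to decide.

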5.2.3 Clinical Evaluations/Procedures

Scheduled of protocol visits and procedures are outlined in Table 5. At the screening visit a qualified study clinician will perform a history and physical for each participant. A complete medication history will be obtained including all drug allergies, immunization history, prescription, over the counter, herbal treatments, contraception use history. Vital signs will include height, weight, blood pressure, pulse, respiratory rate and temperature.

5.2.3.1 Specimen collection

All pharmacological samples must be collected as per protocol-specified schedule. Each protocol-specified pharmacological sampling visit will have a window of up to 3 days (up to week for hair) for sample collection. The following pharmacological samples will be collected as follows:

Blood collection

A blood sample will be obtained at protocol specified visits to process plasma, whole blood, DBS, and PBMCs. On a given study day blood collection, up to 21-mL draw with no planned timing relationship with dosing. The blood will be collected from an arm vein by trained clinic staff according to study site policies and procedures.

The schedule of protocol visits and procedures are outlined in Table 5.

Table 5: Schedule of protocol visit schedule and procedures.

	Screening	Entry	DOT PrEP Period (weeks)										Post DOT Period	
Timeline (weeks)			W1		W2	W3	W4	W5	W6	W7	W8	W9	W10-16	
			Day 4	Day 7										
Clinic Visits #		1	2	3	4	5	6	7	8	9	10	11	12	
Procedure														
Informed consent	x													
Medical, sexual, contraception, antenatal history review, vaccine history	x	x	x	x	x	x	x	x	x	x	x			
Physical and obstetric exam ^a	x													
Fetal ultrasound for pregnant women*	x													
Dispense back up PrEP medication ^e		x												
Issue medical calendar		x												
AE assessment		x	x	x	x	x	x	x	x	x	x			
Safety Labs ^{a,c}	x	[x]									x			
Urine β HCG ^a	x	[x]					x				x			
HBS Ag	x													
HIV-1 rapid test ^a	x	[x]					x				x			
Hair collection							x				x		x	
hDNA		x		x										
Study Bloodwork ^d (WB, plasma, DBS, PBMC)**		x	x	x	x	x	x	x	x	x	x	x	x	
Vaginal tissue- non-pregnant only ^f			x	x			x				x			
Vaginal swab		x	x	x			x				x			
DBS by fingerstick			x	x			x				x			
Study Urine ^d		x	x	x	x	x	x	x	x	x	x	x	x	
Concomitant Medication Review	x	x	x	x	x	x	x	x	x	x	x			
STI testing		x												
DOT ^b		x	x	x	x	x	x	x	x	x	x			

[x] Indicated if screening occurred more 30 days before planned enrollment. The screen and entry visits must be ≤ 30 days apart.

*If women has no record of fetal ultrasound for the current pregnancy, ultrasound must be conducted before enrollment.

**Blood works for pregnancy women only at week 0, 1, 2, 4, 6, 8, 9

a. Safety labs or vitals can be performed as needed at any time

b. DOT performed if applicable per randomization schedule

- c. Protocol-specified safety labs include: CBC, HBAg, Creatinine clearance, in addition to monthly HIV testing and urine pregnancy tests.
- d. Study Bloodwork: WB, DBS, PBMC, plasma and all available blood cell types; Study Urine: endogenous molecules such as nucleosides.
- e. Study medications will be dispensed as described
- f. Random subset (50%) on day 4 and the remaining subset (50%) on day 7

Vaginal swab and tissue

We will obtain vaginal swab for all cisgender women and, in non-pregnant cisgender women, vaginal tissue i.e., only non-pregnant cisgender women will have tissue biopsy. Obtaining vaginal swabs does not impose unnecessary risks in pregnancy and does not stimulate labor. Vaginal biopsies will be taken with a 2.3 x 4.2-mm Tischler gold-plated gynecological forceps. Biopsies will be immediately placed in a pre-weighed and pre-labeled cryovial, subsequently reweighed and immediately stored at -80°C until analysis⁵⁹.

Justification for vaginal tissue sampling: Vaginal mucosa is the tissue of relevance to the acquisition of HIV infection for cisgender women. The planned sampling schedule will help to define early drug kinetics and how soon drugs accumulate in vaginal tissue following PrEP initiation in first the week until steady states. To minimize risk associated with this procedure and burden on cisgender women, we will ensure each woman will have only one biopsy in a 4 week-period by sampling separate cisgender women at day 4 and day 7 (Week 1); Thus in week1, only 50% non-pregnant cisgender women will have tissue sample obtained at day 4 and the other half will be sampled day 7. Sample collection at weeks 4 and 8 will be obtained from all non-pregnant cisgender women.

Urine testing

Urine samples will be obtained at periodic intervals for future testing to help refine models for prediction of adherence in cisgender women using urine. The participant will be asked to void a small amount of urine into a sterile specimen container per standard procedures.

Hair collection

A small amount of hair (about 50-100strands) will be collected from the occipital portion of the scalp refine models for prediction of long-term adherence in cisgender women using hair. The hair is cut from as close to the scalp as possible with scissors. The hair that is cut will be taken from underneath the top layer of hair to minimize the ability to see where the hair was cut from. Measuring TFV/FTC exposure in small hair samples is feasible and acceptable in Kenya PrEP trials⁵⁵.

Blood for DNA

Blood for DNA will be obtained at the week 1 visit for those who consent for sample storage for future testing. Genomic DNA will be isolated using a commercially available kit, according to standard manufacturer protocol. The DNA will be for pharmacogenetic studies of protein drug transporters described in this protocol and not for whole genome sequencing. Only gene DNA analysis related to antiretroviral drug disposition or treatment response (drug transporters) will be evaluated. An addendum consent will be used to obtain informed consent for future testing.

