4.7 Toxicity Management

Safety related laboratory testing will be performed at study entry and at week 8 and or as indicated by clinician during follow up. If enrollment occurs more 30 days after screening, entry safety labs will be repeated (HIV rapid testing, Complete blood count, HBV surface antigen, serum creatinine, urine pregnancy tests. Toxicity will be managed in consultation with a clinician on the protocol. The clinician may discontinue the study drug at any time if he/she feels that continued use would be harmful to the participant. The PSRT should be consulted when possible. The PSRT will be consulted when considering further holding or recommencing study medication.

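### The entry HIV test is conditional on a delay the 30-day entry limit forbids, so as scheduled a woman may start PrEP on an HIV result up to 30 days old

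*Combined protocol and SAP*

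**What the plan says.** **The schedule.** Table 5 (section 5.2.3.1) marks the HIV rapid test x at screening, week 4 and week 8, but [x] at entry. The footnote explains the bracket: "Indicated if screening occurred more 30 days before planned enrollment. The screen and entry visits must be ≤ 30 days apart". Section 4.7 opens with "Safety related laboratory testing will be performed at study entry and at week 8", then makes the repeat, HIV included, conditional: "If enrollment occurs more 30 days after screening, entry safety labs will be repeated".

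**The time limit.** Section 5.2 states "Enrollment must occur within 30-day screening window". Section 5.2.2 repeats the limit in the entry visit's own heading, and 5.1 sends anyone who misses the window back to be re-screened.

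**The first dose.** The Clinic visit 1 list in 5.2.2 includes a urine pregnancy test, STI tests and "DOT: Witness first PrEP dose". It names no HIV test. The next visit whose list names one is "Clinic visit 6: Week 4 (Dose 28) visit".

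**Text that points the other way.** Section 4.8 asks that HIV rapid testing be finished before study medication is given. Sections 8.4 and 8.5 promise an HIV test at baseline and every four weeks after that; baseline is not defined.

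**The concern.** The condition for the entry test and the limit on entry exclude each other, so the bracketed test looks scheduled but is not. Section 4.8 gives the purpose of frequent testing as stopping drug promptly in an infected participant so that resistant virus is less likely to emerge. Starting two-drug PrEP in a woman with an unrecognised infection is the event this should prevent, and the first dose is the one point in the dosing period with no scheduled test.

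The gap applies to all three non-pregnant arms (up to 54 women) and to the pregnant cohort (up to 18). It matters most for the pregnant cohort, who are enrolled because they are at elevated HIV risk. Section 3.2 excludes current or past PrEP users, so these women are not on PrEP between screening and entry.

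**Working it through.** The plan gives no figure for the longest gap between HIV tests beyond monthly or every four weeks. On drug that figure reproduces: from Dose 28 to Dose 56 is 28 days.

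**Inputs.** Screening-to-entry limit: 30 days (Table 5 footnote, 5.1, 5.2, 5.2.2). Trigger for the entry test: more than 30 days (Table 5 footnote, 4.7). First dose: at entry (5.2.2). Next scheduled HIV test: week 4, Dose 28 (5.2.2). Visit window: "Each protocol-specified clinic visit will have a window of up to three days for sample collection". Cohort sizes: 54 and 18 (2.6).

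**1. Can the trigger fire?** Trigger: lag > 30 days. Permitted: lag ≤ 30 days. No lag meets both. A woman who passes 30 days must be re-screened. That supplies a new HIV test under 5.1, but it starts a new 30-day window, so the bracketed entry test is again not due.

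**2. Age of the result at first dose.** 0 to 30 days.

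**3. Gap between scheduled tests.** Gap = lag + time from entry to the week 4 test. That time is 27 days if Dose 1 is on entry day and the test is at Dose 28, or 28 days if week 4 means 28 days after entry.

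| Screening-to-entry lag | Gap between scheduled tests |
|---|---|
| 0 days | 27–28 days |
| 14 days | 41–42 days |
| 28 days | 55–56 days |
| 30 days | 57–58 days |

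Worst case against the on-drug interval: 57/28 = 2.04 and 58/28 = 2.07. If the 3-day window also applies to the HIV test, the worst case is 60 or 61 days. The like-for-like comparison then puts 3 days on both sides: 60/31 = 1.94 and 61/31 = 1.97. Either way the ratio is about 2.

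**4. Drug taken before the week 4 test by a woman already infected at entry.** Daily dosing: 27 doses, or 28 if 28 days elapse. Four per week: at most 4 × 4 = 16. Two per week: at most 2 × 4 = 8.

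**5. Expected infections between screening and entry, pregnant cohort.** Incidence is assumed at 4% to 6% per year, from the levels cited in 1.1.1 and 1.2.1, taken as annual.
- All 18 wait 30 days: 18 × 30/365 = 1.48 person-years; × 0.04 = 0.059; × 0.06 = 0.089.
- Assumed mean wait of 15 days: 18 × 15/365 = 0.74 person-years; × 0.04 = 0.030; × 0.06 = 0.044.

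These are upper bounds on what an entry test would find, since a rapid test can miss very recent infection. The documents give no incidence for low-risk women, so none is computed for the 54.

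**6. With an unconditional entry test.** The result is 0 days old at first dose. The next test is 27 to 28 days later (30 to 31 with the window), in line with a four-week interval.

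**The case against.** **The protocol already calls for a pre-dose test.** The first dose is study medication, so 4.8 read naturally covers it, and the opening of 4.7 puts safety labs at entry. This stands in part: the likely intent is to test, and Table 5 is out of step. But 4.8 sets no maximum age for the result, 4.7 goes on to make the repeat conditional, and 9.1 ties the HIV test to screening volunteers. Staff working from Table 5 or the visit list are not told to test. A reader might infer that the protocol as a whole dispenses with a pre-dose test; 4.8 does not support that.

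**Baseline may mean screening.** Section 8.5 groups baseline HIV testing with hepatitis B, whose own row in Table 5 is marked at screening only. On that reading, with the four weeks counted from enrolment, 8.4 and 8.5 can be met. The roughly doubled first gap remains.

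**The gap overstates drug exposure.** This stands. Up to 30 of the 57 to 58 days come before any drug. A reader might infer that time on drug while infected is doubled. It is not: at most 27 to 28 days pass on drug before the week 4 test, no longer than the normal interval, and a woman infected just after a negative entry test would have about the same exposure. What the missing test adds is the chance of starting drug while already infected.

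**Other safeguards exist.** Suspected acute HIV is an exclusion (3.2), history is reviewed at entry, extra tests are allowed as needed (Table 5 footnote a, 8.5), and non-pregnant women at high risk are excluded. These lower the risk, but none requires an entry test. The study-specific procedures manual, not among these documents, may add one.

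**The visit list is not exhaustive.** It also omits the adverse event assessment that Table 5 marks at entry, so its silence on HIV is supporting evidence only. It does, however, require without condition the urine pregnancy test that Table 5 brackets in the same way.

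**Conclusion.** The point holds as a gap in the testing schedule and an inconsistency within the protocol. No enrolment that follows the rules triggers the bracketed entry test, so a compliant site can give the first dose on an HIV result up to 30 days old. The 57 to 58 days is a worst case at a 30-day lag, not a typical interval. The conflict with 4.8 rests on reading its rule to cover the first dose, which is the natural reading; the conflict with 8.4 and 8.5 holds only if baseline means entry.

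The expected count is very small: 0.06 to 0.09 at most in the pregnant cohort under the assumed incidence, and about half that at a 15-day mean wait. A reader might also infer a threat to the week 8 primary sample, because 3.8 does not replace seroconversions. At these counts the effect is negligible, and 3.8 does not say that an infection already present at entry counts as a seroconversion. The case for change rests on the harm to an individual woman if it happens, on the protocol's own reasoning in 4.8, and on the low cost.

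**What to change.** Make the HIV rapid test at entry unconditional, with a negative result required before the first dose; a screening test done the same day can serve. In the text:

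- Table 5: change [x] to x for the HIV rapid test at Entry.
- Section 5.2.2: add the HIV rapid test to the Clinic visit 1 list, before the witnessed dose.
- Section 4.7: replace the over-30-day repeat rule with the re-screening rule in 5.1.
- Sections 8.4 and 8.5: state that baseline, for HIV testing, means the entry visit.

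The cost is protocol wording and at most 72 additional rapid tests, at a visit that already draws pre-drug blood.
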